#### Statistical Plan:

Correlative endpoints such as systemic inflammatory, immune markers, and expression of PLK and changes from pre- to post-treatment will be summarized using descriptive statistics.

Changes from baseline vs. follow-up time points will be assessed using paired test methodologies. WES data will be processed using the data processing and data analysis pipelines from the Biostatistics and Bioinformatics shared resource of Markey Cancer Center to identify candidate mutated genes with adjustment for false discovery rate.

## **9.6 Reporting and Exclusions**

### **9.6.1 Evaluation of Toxicity**

The Safety Population is defined as all patients who received at least one dose of study treatment. Analyses of safety and toxicity will be based on the Safety Population. Safety and toxicity will be assessed through the frequency and percent of AEs, SAEs, DLT, and AEs of special interest (AESIs). Toxicity will be assessed using Common Terminology Criteria for Adverse Events v 5.0 (CTCAE). Safety and toxicity will also be assessed by patient-reported outcomes and adverse events (PRO-CTCAE) captured by digital instruments every 2 weeks until Week 28 for acute toxicity for monitoring of acute and long-term toxicity.

### **9.6.2 Evaluation of Response**

The Per Protocol Population is defined as all patients who are in the Safety Population and have no major protocol violations that could influence the assessment of efficacy. Efficacy analysis, including the analysis of primary and secondary endpoints (excluding safety and toxicity), will be based on the Per Protocol Population.

Responses to treatment will be evaluated per PCWG3 criteria as described in Section 12.1 (for bone lesions).

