### 5.10.2.2.2 Timing of Assessment

Pain at baseline and analgesic use (pre-treatment, Week 0) will be measured via serial (daily) assessments in a 7-day run-in period. Patients will be considered evaluable if they complete assessments on  $\geq 4$  days within the 7-day run-in period. During treatment, pain and analgesic use will be measured every 2 weeks through Week 28, followed by routine clinic follow-up until 1 year or when patients experience new pain. Complete pain assessments via the full BPI-SF (Appendix D) will be collected at baseline, after Cycle 1, after Cycle 2, and at Week 28. Pain assessments will be halted at the patient's request or if the patient discontinues study treatment for reasons other than disease progression.

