### 9. STATISTICAL CONSIDERATIONS

#### 9.1 Study Design/Endpoints

This is a single-arm, open-label phase 2 study to evaluate the efficacy of Sn-117m-DTPA on

sustained pain response in patients with CRPC metastatic to at least two bone sites, with at least one clinically meaningful pain at baseline ( $\geq 4$  on an 11-point pain intensity scale). Sustained pain-response is defined as: 1) achieving pain index  $\leq 3$  within a 12-week period and 2) maintaining that pain index  $\leq 3$  over a 16-week time period (beginning when the pain index  $\leq 3$  is initially achieved). The maximum duration of follow-up required to declare a patient a responder is 28 weeks, representing a patient who initially achieves pain index  $\leq 3$  toward the end of the 12-week period and is followed for an additional 16 weeks to confirm maintenance of pain index  $\leq 3$ .

Eligible patients will be assigned to receive Sn-117m-DTPA at 20 mCi/70 kg (0.28 mCi/kg) every 8 weeks for two cycles. Treatment will last for 16 weeks with two treatment injections given at 8-week intervals. The study utilizes a mini-max Simon two-stage design to assess anti-tumor activity and pain benefit of Sn-117m-DTPA.

Patients are not allowed to receive external radiation within 12 weeks from the start of treatment administration. If their pain index does not reach  $\leq 3$  after 12 weeks, they are not meeting the primary endpoint, and they can then get external radiation for pain control.

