The sustained pain response rate under null hypothesis is  $p_0=0.1$  and the alternative hypothesis is  $p_1=0.3$ . The literature on sustained pain-relieving benefit with radiopharmaceutical drugs in prostate cancer with bone metastases is limited. Nilsson *et al.* studied the dose-response relationship and pain-relieving effect of radium-223 (Nilsson *et al.*, 2012). Pain response at Week 8 was seen in 40% of patients. The null hypothesis for sustained pain response in the absence of effective therapy and a strong literature support would assume 10%. We propose that the sustained pain response with Sn-117mDTPA would achieve 30%. Using the mini-max Simon's two-stage design, the total sample size is 25 patients, with 10 patients for the first stage and 15 patients for the second stage. If 1 or 0 patients achieve sustained pain response in the first stage, the study will be stopped early for futility; otherwise the trial continues to the second stage. If 5 or fewer patients achieve sustained pain-response, then no further investigation of the study treatment is warranted. This design has an estimated 5% type I error rate and 80% power. The planned sample size and interim analysis has a 3.28% actual type I error rate and 80.17% actual power. The probability of stopping at the end of the first stage is about 55% under the null hypothesis. Study enrollment will be interrupted for the interim efficacy analysis.

The efficacy primary endpoint will also be summarized by the point estimation of the ORR with the corresponding 95% confidence intervals. Patients who received any amount of study drug will be included in the denominator for the calculation of ORR.

Summary statistics on safety endpoints will be calculated and reviewed at the interim analysis or anytime during the study at the investigator's discretion. If there is statistically significant evidence that the DLT probability exceeds 30%, the study should be suspended for further review. A 95% exact binomial confidence interval will be calculated for the DLT rate. If the observed lower bound of the confidence interval exceeds 30%, we consider it statistically significant evidence that the DLT probability exceeds 30%.

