#### 9.4.2 Overall Response Rate

A Fisher's exact 95% confidence interval will be calculated for the overall response rate. The denominator will include all patients who received at least one dose of study treatment and do not have major protocol deviations. Patients who do not have observed clinical response will be counted as negative responses.

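### The primary endpoint has two incompatible analysis sets (all treated in 9.1, Per Protocol in 9.6.2); a lesser gap is that pain scoring can stop before response can be confirmed

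*Combined protocol and SAP*

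**What the plan says.** **Analysis set.** Section 9.1 says the primary efficacy endpoint will be summarized by a rate with a 95% confidence interval, and then: "Patients who received any amount of study drug will be included in the denominator for the calculation of ORR". Section 9.6.2 says: "Efficacy analysis, including the analysis of primary and secondary endpoints (excluding safety and toxicity), will be based on the Per Protocol Population". It defines that population as the Safety Population less patients with major violations capable of affecting the efficacy assessment. It does not say which violations are major. Neither section is labelled as the main or the sensitivity analysis. Section 9.4.2, for the secondary overall response rate, sides with 9.6.2: "The denominator will include all patients who received at least one dose of study treatment and do not have major protocol deviations".

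**Decision rule.** The go/no-go decision in 9.1 is a fixed count: "If 5 or fewer patients achieve sustained pain-response, then no further investigation of the study treatment is warranted". Section 9.2 times the interim by the first 10 patients to become evaluable. That word is tied to the run-in diary in 5.10.2.2.2 and to tumor response in 12.2.1, but never to follow-up for sustained pain response.

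**Pain scoring.** Section 5.10.2.2.2 schedules pain and analgesic reports every two weeks through Week 28. It halts them at the patient's request or "if the patient discontinues study treatment for reasons other than disease progression". Response must be held for 16 weeks from when it is first reached, and 9.1 adds: "The maximum duration of follow-up required to declare a patient a responder is 28 weeks".

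**The concern.** A single-arm trial of 25 patients has one primary number, and the plan gives two rules for its denominator. Because the trial is open-label and *major* is undefined, someone may have to decide who leaves the Per Protocol set with outcomes already known.

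The removal can also be tied to outcome. Section 9.1 says: "Patients are not allowed to receive external radiation within 12 weeks from the start of treatment administration". A patient irradiated for pain in that window has breached the protocol and has probably not responded. Section 9.1 keeps this patient as a failure; 9.6.2 could remove the patient.

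The halting clause raises a smaller question about the same endpoint. If scores stop when treatment stops, a patient who had responded may have no data from which to confirm it.

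**Working it through.** **Inputs (9.1).** Null rate 0.10, alternative 0.30, 25 patients in stages of 10 and 15. Stop if 1 or fewer respond in stage 1; go if 6 or more respond in total.

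**Step 1: the plan's own figures.** With stage sizes n1 and n2,

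P(go | p) = Σ over x = 2..n1 of C(n1,x) p^x (1−p)^(n1−x) · P[Bin(n2,p) ≥ 6−x]

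| Stages | Type I error | Power | Early stop under null |
|---|---|---|---|
| Stated in 9.1 | 3.28% | 80.17% | about 55% |
| 10 + 15, as written | 2.77% | 74.00% | 73.6% |
| 15 + 10 | 3.28% | 80.17% | 54.9% |

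The stated figures belong to 15 + 10. That is a separate matter. Both splits are carried below only because the starting power differs.

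**Step 2: reported rate.** Exact (Clopper-Pearson) limits are Beta⁻¹(0.025; x, n−x+1) and Beta⁻¹(0.975; x+1, n−x).

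| Case | Rate | 95% CI | Six or more? |
|---|---|---|---|
| 6 responders, all treated | 6/25 = 24.0% | 9.4 to 45.1 | yes |
| two non-responders dropped | 6/23 = 26.1% | 10.2 to 48.4 | yes |
| one responder dropped | 5/24 = 20.8% | 7.1 to 42.2 | no |

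Removing non-responders cannot change a count of responders. Only removal of a responder can. Without replacement, the change then runs one way: go among all treated, no-go in Per Protocol.

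**Step 3: power, on assumed exclusions.** The documents give no violation rate. Suppose k patients are excluded from stage 2 regardless of response, with no replacement and the cut-off kept at six. Then n2 becomes 15−k or 10−k.

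| k | Power, 10 + (15−k) | Loss | Power, 15 + (10−k) | Loss |
|---|---|---|---|---|
| 0 | 74.0% | – | 80.2% | – |
| 1 | 71.5% | 2.5 points | 76.8% | 3.4 points |
| 2 | 68.5% | 5.5 points | 72.9% | 7.2 points |
| 3 | 65.0% | 9.0 points | 68.6% | 11.6 points |

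Per Protocol responders are then a subset of treated responders. Each loss is therefore also the chance, at a true 30% rate, that the two sections give opposite decisions. Type I error falls from 2.8% to 2.4%, 2.0% and 1.6%, or from 3.3% to 2.7%, 2.2% and 1.8%.

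**Step 4: timing of the halting clause.**
- The first post-baseline score is at Week 2, so the earliest confirmation is 2 + 16 = Week 18. The latest is 12 + 16 = Week 28.
- The second injection is due at Week 8. With the longest delay in Section 7 it falls at 8 + 8 = Week 16, an outer limit because a four-week limit also applies to unresolved hematological toxicity.
- A responder who stops before the second injection therefore stops before Week 18 and generally cannot be confirmed. The single off-study pain score in the Section 11 calendar does not cover the gap.

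**The case against.** **The label in 9.1.** ORR could be read as the separate response rate of 9.4.2, which would remove the conflict. This fails: the preceding sentence in 9.1 names the primary endpoint, and 9.4.2 has its own denominator.

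**The power losses.** A reader might take 2.5 to 11.6 points as the expected chance of conflicting decisions. The documents do not support that. The one outcome-related route visible in the text, early radiation in a patient who has not responded, removes non-responders and costs no power. The losses need exclusion regardless of response, all in stage 2, without replacement, and 9.2 leaves replacement open.

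**The confidence limits.** A reader might also infer that the choice of set decides significance, because the lower limit moves from 9.4% to 10.2% across the 10% null. The go/no-go rule does not use the interval.

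**Loss of follow-up.** It is tempting to read 6.4 and 6.5 as abandoning patients who stop treatment. The encouragement in 6.4 to attend safety visits concerns withdrawn patients who will return for no further visits. The general schedule in 6.5 runs to Week 28 with no exception for stopping treatment. What stands is narrower: 5.10.2.2.2 halts the pain reports even though 6.5 keeps the visits. A DLT after both planned injections leaves no planned injection to stop, so the gap mainly concerns patients who stop between the two.

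**Missing confirmation.** The definition in 9.1 already implies that an unconfirmed patient is not a responder. That is fair, but it is not written as a scoring rule. The explicit one sits in 9.4.2, for the secondary rate: "Patients who do not have observed clinical response will be counted as negative responses".

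**All-treated has its own bias.** This objection stands and shapes the fix. Section 6.3.1 permits other systemic therapy from 8 weeks after the last injection. After a single injection that is about Week 8, ahead of any confirmation. Relief from such therapy, or from external radiation, could be credited to Sn-117m-DTPA unless a rule prevents it.

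**Conclusion.** The contradiction between 9.1 and 9.6.2 is certain on the text and should be fixed. Its demonstrated effect is on the reported rate and interval: 24.0% against 26.1% when two non-responders leave. The decision changes only if a responder is excluded. The exclusion counts, and the power figures built on them, are assumptions.

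A reader might infer that Per Protocol analysis inflates the false-positive rate. With a fixed count and no replacement it does the opposite. If excluded non-responders were replaced, that reassurance would no longer follow, which is a reason to settle replacement now.

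The halting clause is minor. It is conservative, since lost confirmations count against the drug. It probably affects few patients, as Section 2 describes severe toxicity as uncommon and tolerability as good. No rate of early stopping is given, so no power figure is attached to it. It still discards primary-outcome data without need.

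**What to change.** 1. **9.6.2 and 9.2.** Make the primary analysis, and the interim count, all patients who received any Sn-117m-DTPA, without replacement, matching 9.1.
2. **Scoring rule for the primary endpoint.** Count as non-responders patients whose sustained response is unconfirmed, and patients who receive external radiation or other new pain-directed or anti-cancer therapy before confirmation. Analgesic changes stay within the pain index. This is a rule for scoring only; it does not alter what treatment a patient may receive.
3. **Per Protocol.** Keep it as a sensitivity analysis, with major violations listed in advance.
4. **5.10.2.2.2.** Continue the two-weekly pain and analgesic reports, by app or paper, to Week 28 after treatment discontinuation unless the patient declines. Reconcile this with the follow-up wording in 6.4 and 6.5.
5. **9.4.2 (optional).** Align the secondary denominator for consistency.

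The cost is wording in these sections and some site effort to obtain reports from patients off treatment, some of whom will decline. The reported rate may be lower than the Per Protocol rate.

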## **10. ADVERSE EVENTS: LIST AND REPORTING REQUIREMENTS**

The prompt reporting of adverse events is the responsibility of each investigator engaged in clinical research, as required by Federal Regulations. Adverse events must be described and graded using the terminology and grading categories defined in the NCI's Common Terminology Criteria for Adverse Events (CTCAE), Version 5.0. The CTCAE is available at [https://ctep.cancer.gov/protocolDevelopment/electronic\\_applications/ctc.htm](https://ctep.cancer.gov/protocolDevelopment/electronic_applications/ctc.htm). Attribution to protocol treatment for each adverse event must be determined by the investigator and reported on the required forms. Please refer to the NCI Guidelines: Adverse Event Reporting Requirements for further details on AE reporting procedures.

Adverse event (AE) monitoring and reporting is a routine part of every clinical trial. The following list of AEs (Section 10.1) and the characteristics of an observed AE (Sections 10.2 and 10.3) will determine whether the event requires expedited reporting via the CTEP Adverse Event Reporting System (CTEP-AERS) **in addition** to routine reporting.

### **10.1 Comprehensive Adverse Events and Potential Risks List (CAEPR)**

### 10.1.1 CAEPR for CTEP IND Agent

#### 10.1.1.1 CAEPR for Sn-117m-DTPA

**Comprehensive Adverse Events and Potential Risks list (CAEPR)  
for  
Stannic-117m Pentetate (Sn-117m-DTPA, NSC 824376)**

The Comprehensive Adverse Events and Potential Risks list (CAEPR) provides a single list of reported and/or potential adverse events (AE) associated with an agent using a uniform presentation of events by body system. In addition to the comprehensive list, a subset, the Specific Protocol Exceptions to Expedited Reporting (SPEER), appears in a separate column and is identified with bold and italicized text. This subset of AEs (SPEER) is a list of events that are protocol specific exceptions to expedited reporting to NCI (except as noted below). Refer to the 'CTEP, NCI Guidelines: Adverse Event Reporting Requirements' [http://ctep.cancer.gov/protocolDevelopment/electronic\\_applications/docs/aeguidelines.pdf](http://ctep.cancer.gov/protocolDevelopment/electronic_applications/docs/aeguidelines.pdf) for further clarification. The CAEPR does not provide frequency data; refer to the Investigator's Brochure for this information. Below is the CAEPR for Stannic-117m Pentetate (Sn-117m-DTPA).

**NOTE:** Report AEs on the SPEER **ONLY IF** they exceed the grade noted in parentheses next to the AE in the SPEER. If this CAEPR is part of a combination protocol using multiple investigational agents and has an AE listed on different SPEERs, use the lower of the grades to determine if expedited reporting is required.

Version 1.0, July 24, 2020^1

Adverse Events with Possible Relationship to Stannic-117m Pentetate (Sn-117m-DTPA) (CTCAE 5.0 Term)	Specific Protocol Exceptions to Expedited Reporting (SPEER)
GASTROINTESTINAL DISORDERS	
Nausea	Nausea (Gr 2)
INVESTIGATIONS	
Lymphocyte count decreased	Lymphocyte count decreased (Gr 2)
Neutrophil count decreased	
Platelet count decreased	
White blood cell decreased	White blood cell decreased (Gr 2)

This table will be updated as the toxicity profile of the agent is revised. Updates will be distributed to all Principal Investigators at the time of revision. The current version can be obtained by contacting [[contact]](mailto:[contact]). Your name, the name of the investigator, the protocol and the agent should be included in the e-mail.

**Note:** Stannic-117m Pentetate (Sn-117m-DTPA) in combination with other agents could cause an exacerbation of any adverse event currently known to be caused by the other agent, or the combination may result in events never previously associated with either agent.

### 10.2 Adverse Event Characteristics

- CTCAE term (AE description) and grade:** The descriptions and grading scales found in the revised NCI Common Terminology Criteria for Adverse Events (CTCAE) version 5.0 will be utilized for AE reporting. All appropriate treatment areas should have access to a copy of the CTCAE version 5.0. A copy of the CTCAE version 5.0 can be downloaded from the CTEP website

[http://ctep.cancer.gov/protocolDevelopment/electronic\\_applications/ctc.htm](http://ctep.cancer.gov/protocolDevelopment/electronic_applications/ctc.htm)

- **For expedited reporting purposes only:**
  - AEs for the agent that are ***bold and italicized*** in the CAEPR (*i.e.*, those listed in the SPEER column, Section 10.1) should be reported through CTEP-AERS only if the grade is above the grade provided in the SPEER.
  - Other AEs for the protocol that require expedited reporting are outlined in Section 10.3.4.
- **Attribution of the AE:**
  - Definite – The AE is *clearly related* to the study treatment.
  - Probable – The AE is *likely related* to the study treatment.
  - Possible – The AE *may be related* to the study treatment.
  - Unlikely – The AE is *doubtfully related* to the study treatment.
  - Unrelated – The AE is *clearly NOT related* to the study treatment.

## 10.3 Expedited Adverse Event Reporting

### 10.3.1 Rave-CTEP-AERS Integration

The Rave Cancer Therapy Evaluation Program Adverse Event Reporting System (CTEP-AERS) integration enables evaluation of post-baseline AEs entered in Rave to determine whether they require expedited reporting, and facilitates entry in CTEP-AERS for those AEs requiring expedited reporting.

All AEs that occur after baseline are collected in Medidata Rave using the Adverse Event form, which is available for entry at each treatment or reporting period, and used to collect AEs that start during the period or persist from the previous reporting period. The CRA will enter AEs that occur prior to the start of treatment on a baseline form that is not included in the Rave-CTEP-AERS integration. AEs that occur prior to enrollment must begin and end on the baseline Adverse Event form and should not be included on the standard Adverse Events form that is available at treatment unless there has been an increase in grade.

Prior to sending AEs through the rules evaluation process, site staff should verify the following on the Adverse Event form in Rave:

- The reporting period (course/cycle) is correct, and
- AEs are recorded and complete (no missing fields) and the form is query-free.

The CRA reports AEs in Rave at the time the Investigator learns of the event. If the CRA modifies an AE, it must be re-submitted for rules evaluation.

Upon completion of AE entry in Medidata Rave, the CRA submits the AE for rules evaluation by completing the Expedited Reporting Evaluation form. Both NCI and protocol-specific reporting rules evaluate the AEs submitted for expedited reporting. A

report is initiated in CTEP-AERS using information entered in Medidata Rave for AEs that meet reporting requirements. The CRA completes the report by accessing CTEP-AERS via a direct link on the Medidata Rave Expedited Reporting Evaluation form.

In the rare occurrence that Internet connectivity is lost, a 24-hour notification is to be made to CTEP by telephone at [contact]. Once internet connectivity is restored, the 24-hour notification that was phoned in must be entered immediately into CTEP-AERS using the direct link from Medidata Rave.

Additional information about the CTEP-AERS integration is available on the CTSU website:

- Study specific documents: Protocols > Documents > Education and Promotion, and
- Expedited Safety Reporting Rules Evaluation user guide: Resources > CTSU Operations Information > User Guides & Help Topics.

NCI requirements for SAE reporting are available on the CTEP website:

- NCI Guidelines for Investigators: Adverse Event Reporting Requirements is available at  
[https://ctep.cancer.gov/protocolDevelopment/electronic\\_applications/docs/aeguidelines.pdf](https://ctep.cancer.gov/protocolDevelopment/electronic_applications/docs/aeguidelines.pdf).

